### **7.4.2 Recording Adverse Events**

Adverse events are to be recorded on the AE eCRF. Severity of an AE will be graded according to the following definitions:

- Mild: The subject experiences awareness of symptoms but these are easily tolerated or managed without specific treatment.
- Moderate: The subject experiences discomfort enough to cause interference with usual activity, and/or the condition requires specific treatment.
- Severe: The subject is incapacitated with inability to work or do usual activity, and/or the event requires significant treatment measures.

Action taken will be categorized as dose not changed, dose reduced, drug interrupted, drug withdrawn, required concomitant medication, required concomitant procedure, and/or other.

Event outcome at resolution or time of last follow-up will be recorded as not recovered/not resolved, recovered/resolved, recovered/resolved with sequelae, recovering/resolving, fatal, or unknown.

#### **7.4.3 Assessment of Adverse Events**

The relationship of an AE to the study medication (tenapanor or placebo) should be determined by the Investigator according to the following criteria:

- Not related: The event is most likely produced by other factors such as the subject's clinical condition, intercurrent illness, or concomitant medications, and does not follow a known response pattern to the study medication, or the temporal relationship of the event to study medication administration makes a causal relationship unlikely.
- Possibly related: The event follows a reasonable temporal sequence from the time of medication administration, and is possibly due to medication administration and cannot be reasonably explained by other factors such as the subject's clinical condition, intercurrent illness, or concomitant medications.
- Related: The event follows a reasonable temporal sequence from the time of medication administration, and/or follows a known response pattern to the study medication, and cannot be reasonably explained by other factors such as the subject's clinical condition, intercurrent illness, or concomitant medications.

#### **7.4.4 Following Adverse Events**

All (both serious and non-serious) AEs must be followed until they are resolved or stabilized, or until all attempts to determine resolution of the event are exhausted. The Investigator should use his/her discretion in ordering additional tests as necessary to monitor the resolution of such AEs.

#### **7.4.5 Discontinuation due to Adverse Events**

Any subject who experiences an AE may be withdrawn at any time from the study at the discretion of the Investigator. Subjects withdrawn from the study due to an AE, whether serious or non-serious, must be followed by the Investigator until the clinical outcome of the AE is determined; refer to [Section 8.7](#). The AE(s) should be noted on the appropriate CRFs and the subject's progress should be followed until the AE is resolved or stabilized. A decision to discontinue a subject due to an AE should be discussed with the Medical Monitor. If the AE may relate to overdose of study medication, the IB should be consulted for details regarding any specific actions to be taken.

#### **7.4.6 Pregnancy**

Female subjects must be instructed to discontinue all study medications and inform the study Investigator immediately if they become pregnant during the study.

The Investigator must report any pregnancy to Medpace Clinical Safety within 1 business day of becoming aware of it. The subject must be immediately discontinued from further treatment with study medication. An uncomplicated pregnancy will not be considered an AE or SAE, but all pregnancies will be followed through birth.

Pregnancies are captured if they occur in female subjects or in the sexual partners of male subjects from the time the subject is first exposed to the investigational product until 30 days after last exposure to the investigational product.

Any congenital abnormalities in the offspring of a subject who received study medication will be reported as an SAE. The outcome of any pregnancy and the presence or absence of any congenital abnormality will be recorded in the source documentation and reported to Medpace Clinical Safety.

#### **7.4.7 Serious Adverse Events**

An SAE is any AE occurring from Screening through the end of the study, at any dose that results in any of the following outcomes:

- Death
- A life-threatening adverse drug experience
- Inpatient hospitalization or prolongation of existing hospitalization
- A persistent or significant disability/incapacity
- A congenital anomaly/birth defect

Important medical events that may not result in death, be life threatening, or require hospitalization may be considered an SAE when, based upon appropriate medical judgment, they may jeopardize the subject and may require medical or surgical intervention to prevent any of the outcomes listed in this definition. Examples of such medical events include allergic bronchospasm requiring intensive treatment in an emergency room or at home, blood dyscrasias or convulsions that do not result in inpatient hospitalization, or the development of drug dependency or drug abuse.

Note: SAEs require immediate reporting to Medpace Clinical Safety. See “Reporting Serious Adverse Events” below for details.

#### **7.4.8 Reporting Serious Adverse Events**

In the event of any SAE reported or observed during the study, **whether or not attributable to the study medication**, site personnel will report it to [REDACTED] within 24 hours of the knowledge of the occurrence.

To report an SAE, complete the SAE eCRF in the EDC system for the study. When the form is completed, [REDACTED] will be notified electronically and will retrieve the form. If the event meets serious criteria and it is not possible to access the EDC system, send an email to [REDACTED] [REDACTED] (phone number listed below), and fax/email the completed paper back-up SAE form to [REDACTED] (contact information listed below) within 24 hours of awareness. When the EDC system becomes available, the SAE information must be entered within 24 hours of the system becoming available. Incoming reports are reviewed during normal business hours.

Safety Contact Information:

[REDACTED]

The Investigator is required to submit SAE reports to the IRB/Independent Ethics Committee (IEC) in accordance with local requirements. All Investigators involved in trials using the same investigational product will receive safety alert notifications for onward submission to their local IRB/IEC as required. All reports sent to Investigators will be blinded.

### Follow-Up Reports

The Investigator must continue to follow the subject until the SAE has resolved or until the condition becomes chronic in nature, stabilizes (in the case of persistent impairment), or the subject dies.

Within 24 hours of receipt of follow-up information, the Investigator must update the SAE eCRF in the EDC system for the study and submit any supporting documentation (e.g., subject discharge summary or autopsy reports) to [REDACTED] via fax or e-mail. If it is not possible to access the EDC system, refer to the procedures outlined above for initial reporting of SAEs.

## **7.5 Efficacy Endpoints**

Serum phosphorus levels will be measured at all study visits. The primary efficacy endpoint is the change from baseline in s-P level at Week 4. The efficacy of tenapanor as an adjunctive therapy to phosphate binder therapy will be evaluated based on the difference in mean change from baseline in s-P level at Week 4 between the tenapanor and placebo groups.

The following efficacy endpoints will be analyzed as key secondary endpoints:

- s-P response (achieving an s-P level <5.5 mg/dL) at Week 4
- Relative change from baseline in iFGF23 at Week 4, derived as (iFGF23 at Week 4/baseline iFGF23 – 1)
- Relative change from baseline in cFGF23 at Week 4, derived as (cFGF23 at Week 4/baseline cFGF23 – 1)

Other secondary endpoints to be analyzed include:

- Change from baseline in s-P level at Week 1, Week 2, and Week 3
- s-P response at Week 1, Week 2, and Week 3
- Change from baseline in PTH at Week 4

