### 1.3 Schedule of Assessments and Procedures

	Screening	Run-in Period		Treatment Period				
	Visit 1	Visit 2	Visit 3	Visit 4	Visit 5	Visit 6	Visit 7	Visit 8/ET
	Week -4 to -3	Week -2	Week -1	Day 1	Week 1	Week 2	Week 3	Week 4
Visit Window	-30 to -14 d	-18 to -7 (5-16 days after V1)	-9 to -2 (5-9 days after V2)	1 e (2-9 days after V3)	8 ± 2	15 ± 2	22 ± 2	29 ± 2
Study Procedure								
Informed Consent	X							
Inclusion/ Exclusion Criteria	X			X f				
Demographics	X							
Medical/Surgical History	X			X g				
Prior/Con Meds	X	X	X	X	X	X	X	X
Physical Examination	X							X
Weight (pre-dialysis)	X							X
Height	X							
Vital Signs a	X			X				X
12-lead ECG	X							X
Safety Laboratory Evaluations b	X							X
Serum Phosphorus	X	X *	X	X	X	X	X	X
FSH Test c	X							
Pregnancy Test c	X							X
Randomization				X				
Study Medication Dispense and/or Return				X	X	X	X	X
FGF23 and PTH Blood Sample				X				X
Biomarker Blood Sample				X				X
AE Assessment		X	X	X	X	X	X	X

\* At Visit 2, a serum phosphorus level of <5.5 mg/dL or >10.0 mg/dL does not deem the subject ineligible. However, the subject may be discontinued at the Investigator's discretion.

a Vital signs include sitting or supine blood pressure and pulse, prior to dialysis.

b Safety laboratory evaluations will include the hematology and serum chemistry tests other than the serum phosphorus test listed in Table 7-1.

c FSH (postmenopausal females) and pregnancy tests are performed on all females <60 years of age unless there is a documented method of sterilization, or FSH test confirms post-menopausal status.

d Screening (Visit 1) could be 14 to 30 days (i.e. 2 to 4 weeks) before randomization following the short-interval schedule.

e Day 1 is the randomization day and serves as the reference day for all visits.

f Subjects must continue to meet all applicable inclusion/exclusion criteria before randomization, including the criteria based on the s-P level at Visit 3.

g Record only changes to medical history from Visit 1

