#### **3.2 Secondary Objective**

- To evaluate the effect of tenapanor versus placebo as adjunctive therapy with phosphate binder to lower subject's s-P level to <5.5 mg/dL.
- To evaluate the effect of tenapanor versus placebo as adjunctive therapy with phosphate binder on intact fibroblast growth factor 23 (iFGF23) and c-terminal fibroblast growth factor 23 (cFGF23).
- To evaluate the effect of tenapanor versus placebo as adjunctive therapy with phosphate binder on parathyroid hormone (PTH).

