The prescribed dose should have been unchanged during the last 4 weeks prior to Screening (Visit 1).
9. Serum phosphorus levels must be  $\geq 5.5$  and  $\leq 10.0$  mg/dL at Screening (Visit 1) and the end of the Run-in Period (Visit 3), analyzed at the central laboratory used in the study.
10. Able to understand and comply with the protocol.

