## **8.3 Visit 4 (Day 1)**

- Inclusion/exclusion criteria (assess s-P criteria using the s-P measurement at Visit 3 and confirm other applicable inclusion/exclusion criteria)
- Vital signs (pre-dialysis)
- Serum phosphorus measurement (pre-dialysis)
- Blood collection for biomarker sample (pre-dialysis)
- Blood collection for FGF23 and PTH (pre-dialysis)
- Randomization

- Medical/surgical history (record only changes to medical history from Visit 1)
- Concomitant medications
- Study medication dispensing
- AE assessment

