### **9.4.3 Primary Efficacy Analysis**

The primary efficacy endpoint is the change from baseline in s-P level at Week 4. For this continuous endpoint, the following pair of hypotheses will be tested:

$$H_0: \mu_t = \mu_p$$

versus

$$H_1: \mu_t \neq \mu_p$$

where  $\mu_t$  and  $\mu_p$  denote the mean changes from baseline in s-P level at Week 4 in tenapanor and placebo groups, respectively. As the primary analysis, the treatment comparison of the mean change will be performed using a mixed-effects model for repeated measures (MMRM) on observed cases of the FAS. The MMRM will include type of phosphate binder (sevelamer or non-sevelamer), s-P level at Visit 3 (<7.5 mg/dL or  $\geq$ 7.5 mg/dL), treatment, visit (Week 1 through Week 4), treatment-by-visit interaction as fixed effects; baseline (Visit 4) s-P level and baseline-by-visit as covariates; and subject as a random effect. An unstructured (UN) covariance matrix will be used to model the within-subject errors. The least squares mean of

s-P changes within each treatment group will be reported. The difference in mean s-P changes at Week 4 between the tenapanor and placebo groups, along with the 95% confidence interval (CI), 99% CI, and *p*-value will also be reported.

The efficacy of tenapanor as an adjunctive therapy to phosphate binder therapy will be concluded if the estimated difference between the tenapanor and placebo groups in the mean s-P change from baseline at Week 4 is negative (i.e., <0) and the corresponding two-sided *p*-value  $\leq 0.05$ .

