#### **9.4.4 Secondary Efficacy Analyses**

For binary response endpoints, the s-P response rate (i.e., the proportion of subjects achieving an s-P level <5.5 mg/dL) at each post-baseline visit will be estimated for each treatment group and be compared between the tenapanor and placebo groups with the 95% and 99% CIs. The *p* value will be obtained from the Cochran-Mantel-Haenszel test adjusting for type of phosphate binder (sevelamer or non-sevelamer) and s-P level at Visit 3 (<7.5 mg/dL or  $\geq 7.5$  mg/dL).

The relative change from baseline in iFGF23 (or cFGF23) at Week 4 will be analyzed using an analysis of variance (ANOVA) model with log-transformed relative change at Week 4 as the dependent variable. The model will include type of phosphate binder (sevelamer or non-sevelamer), s-P level at Visit 3 (<7.5 mg/dL or  $\geq 7.5$  mg/dL), and treatment as factors. Back-transformed point estimates and CIs (95% and 99%) will be reported.

Mean changes from baseline in s-P level at Week 1, Week 2, and Week 3 will be estimated for each treatment group and be compared between the tenapanor and placebo groups using the MMRM of the primary analysis.

The change from baseline in PTH at Week 4 will be analyzed using an analysis of covariance (ANCOVA) model with PTH change at Week 4 as the dependent variable. The model will include type of phosphate binder (sevelamer or non-sevelamer), s-P level at Visit 3 (<7.5 mg/dL or  $\geq 7.5$  mg/dL), treatment as factors and baseline PTH level as a covariate.

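### Some randomized subjects may already be below 5.5 mg/dL at the Visit 4 baseline, and the Week 4 s-P response test does not adjust for that baseline value

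*Combined protocol and SAP*

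**What the plan says.** - **Entry.** Inclusion criterion 9 (Section 5.1) requires s-P from 5.5 to 10.0 "mg/dL at Screening (Visit 1) and the end of the Run-in Period (Visit 3), analyzed at the central laboratory used in the study". In the schedule (Section 1.3), a Visit 2 value outside that range "does not deem the subject ineligible". At Visit 4, Section 8.3 tells sites to "assess s-P criteria using the s-P measurement at Visit 3".
- **Baseline.** Visit 4 is Day 1, scheduled "2-9 days after V3" (Section 1.3). Its s-P value is the baseline. The primary MMRM (Section 9.4.3) includes "baseline (Visit 4) s-P level and baseline-by-visit as covariates". No section sets an s-P requirement at Visit 4.
- **Endpoint.** Section 7.5 lists "s-P response (achieving an s-P level <5.5 mg/dL) at Week 4" with no condition on baseline and none on a fall. The matching objective (Section 3.2) compares tenapanor with placebo "as adjunctive therapy with phosphate binder to lower subject's s-P level to <5.5 mg/dL".
- **Test.** Section 9.4.4 takes the p-value from the "Cochran-Mantel-Haenszel test adjusting for type of phosphate binder (sevelamer or non-sevelamer) and s-P level at Visit 3", split at 7.5 mg/dL. Visit 4 s-P does not enter.
- **Set and order.** Efficacy is analysed on the FAS, which does not exclude subjects below 5.5 at baseline (Section 9.3). Week 4 response is step B of the hierarchy in Section 9.4.5 and gates iFGF23 and cFGF23.

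**The concern.** A subject with 5.6 mg/dL at Visit 3, 5.0 at Visit 4 and 5.4 at Week 4 has risen by 0.4 on treatment and is counted as a responder. Selecting on a value at or above 5.5 at Visit 3 means that Visit 4 values will on average fall back, so such subjects are to be expected in both arms.

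The planned strata do little to account for them. The Visit 3 split lies 2.0 mg/dL above the responder cut (7.5 - 5.5), so everyone who enters between 5.5 and 7.5 shares one s-P category. The Visit 4 value, which the trial already collects and already uses in the MMRM, would separate them better. At stake are precision on a gating test, exposure to chance imbalance in that value, and how well the response rates describe lowering to target.

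**Working it through.** **1. The plan's own figure.** Section 9.2 gives SD 1.0, difference -0.5 and 107 per group. Standard error = 1.0 x sqrt(2/107) = 0.1367, and 0.5/0.1367 = 3.657. Normal-approximation power is Phi(3.657 - 1.960) = 95.5% at two-sided 0.05 and Phi(3.657 - 2.576) = 86.0% at 0.01. The t-test gives 95.4% and 85.4%. The stated 95% and at least 85% reproduce. The plan gives no response rates and no power for the responder endpoint.

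**2. How many start below 5.5.** From the documents: SD of change 1.0, effect -0.5, selection to 5.5-10.0 at Visits 1 and 3. With independent visit errors of equal size, 1.0^2 = 2 x sw^2, so sw = 0.707. Assumed, because the documents do not give them: normal s-P, no drift, source mean 5.5 to 7.0, between-subject SD 0.8 to 1.3. Simulated results:

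| Source mean / between-subject SD | Visit 4 <5.5 (of 214) | Response placebo / tenapanor | Responders already <5.5 at Visit 4, placebo / tenapanor | Responders with no fall, placebo / tenapanor |
|---|---|---|---|---|
| 5.5 / 0.8 | 22.4% (48) | 22.5 / 42.0% | 39 / 33% | 20 / 13% |
| 5.5 / 1.0 | 18.3% (39) | 18.3 / 35.3% | 38 / 32% | 19 / 12% |
| 6.0 / 1.0 | 12.9% (28) | 12.9 / 26.9% | 33 / 27% | 17 / 10% |
| 6.5 / 1.0 | 8.5% (18) | 8.5 / 19.2% | 28 / 22% | 14 / 9% |
| 7.0 / 1.0 | 5.1% (11) | 5.1 / 12.6% | 24 / 18% | 12 / 7% |
| 7.0 / 0.8 | 4.6% (10) | 4.6 / 12.3% | 20 / 15% | 10 / 6% |

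The placebo columns can be checked by symmetry. Without drift, Visit 4 and Week 4 have the same distribution, so the placebo response rate equals the share below 5.5 at Visit 4. The no-fall share is half the already-below share (for example 38/2 = 19).

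Visit 4 follows Visit 3 by only 2 to 9 days, so independent errors may overstate the fall-back. With an assumed serial correlation (time constant 14 days, same 4-week change SD), 3 to 10% are below 5.5 at Visit 4 and 6 to 9% of placebo responders show no fall.

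**3. Chance imbalance.** The between-arm difference in the share below 5.5 has SD sqrt(2p(1-p)/107) under simple 1:1 allocation: 3.0 points at p = 0.05, 4.9 at 0.15 and 5.5 at 0.20. Only part of this reaches the response difference. At source mean 6.0 and SD 1.0, placebo response is 33% in subjects below 5.5 at Visit 4 (0.33 x 0.129/0.129) and 9.9% in the rest. A one-SD imbalance of 4.6 points (p = 0.129) therefore moves the rate difference by about 4.6 x (0.33 - 0.099) = 1.1 points, against an expected difference of 26.9 - 12.9 = 14.0.

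**4. Power and level.** Stratified 1:1 trials of 214 subjects, between-subject SD 1.0, shift of -0.5. The first three power columns come from 2,000 trials per scenario, the last from a separate run of 3,000.

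| Source mean | Planned CMH | CMH plus Visit 4 <5.5 stratum | Logistic with Visit 4, Wald test | Planned CMH to logistic score test with Visit 4 |
|---|---|---|---|---|
| 6.0 | 75% | 77% | 79% | 74 to 79% |
| 6.5 | 64% | 65% | 67% | 65 to 70% |
| 7.0 | 51% | 52% | 52% | 52 to 56% |

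Rejection under no effect:
- Planned CMH: 4.3 to 5.2%.
- Score test: 4.8 to 5.8%.
- Wald test: 4.6, 4.0 and 2.6% as the source mean rises and responders become fewer.
- Likelihood-ratio test: 5.5, 6.3 and 6.1% in 4,000 trials per scenario, and up to 6.6% in other runs.

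The Monte Carlo standard error at 3,000 trials is sqrt(0.05 x 0.95/3000) = 0.4 points, so 5.8% is two standard errors above 5%. Moving from CMH to the likelihood-ratio test without Visit 4 already adds 0.7, 0.9 and 1.7 points of power, so part of that test's apparent gain comes from its level.

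**The case against.** Treatment is randomized and blinded, so subjects below 5.5 at Visit 4 fall in both arms by chance, and the test concerns the difference. Attaining a target is a legitimate endpoint: someone at 5.4 mg/dL at Week 4 is at target, and the size of the fall is already the primary endpoint, adjusted for Visit 4. Adjusting for the two randomization factors is standard and is the stated general approach in Section 9.4.7. A model-based test could loosen the gate if it runs above 5%. The percentages rest on inputs that the documents do not supply.

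All of this stands, and it limits the point. A reader might infer that the response comparison is biased, that its type I error is inflated, or that the endpoint is invalid because some responders did not fall. The documents do not support any of these. Randomization removes the first, the planned CMH holds its level, and the objective in Section 3.2 compares arms and need not require a within-subject fall. Nor has it been shown that re-screening after a Visit 3 failure enlarges the problem: the simulations do not include it.

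What the objection does not answer is that a prognostic value already collected is left out of a gating test, while the MMRM uses it and the PTH analysis uses its own baseline.

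Section 9.1 refers to a separate SAP that governs where it differs. Its text is not in the document reviewed and could add such an adjustment, although that section expects no changes to the secondary efficacy analyses.

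**Conclusion.** The point holds as a cheap improvement, not as an error. The entry rule permits baseline values below the responder cut, and the response analysis makes no use of the baseline value. Under the assumed distributions, roughly 5 to 20% of randomized subjects would be affected, fewer with serial correlation. The cost is about 1 to 5 points of power on step B, some unadjusted chance imbalance of modest size, and response rates that match the lowering objective less closely. Confidence in the facts is high. Confidence in the size is moderate, because source mean, between-subject SD, drift and correlation between visits are all assumed, and some of the score test's gain may reflect a level slightly above 5%.

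**What to change.** In Section 9.4.4 and the synopsis, before unblinding:

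1. Make the Week 4 s-P response p-value the score test for treatment from a logistic model with the two stratification factors and continuous Visit 4 s-P. Name that one test. Do not use the likelihood-ratio test.
2. Report the covariate-standardised difference in response rates with 95% and 99% CIs, and take the direction needed for step B of Section 9.4.5 from it.
3. Keep the stratified CMH as supportive.
4. Tabulate by arm the number with Visit 4 s-P below 5.5.
5. Add a supportive analysis in subjects with Visit 4 s-P of 5.5 or above. The FAS remains primary.

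No change to entry criteria, visits or samples is implied. The cost is wording and a few table rows.

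Downsides: a model-based test replaces a table test. Its level may run slightly above 5% when responders are few (up to about 5.8% in simulation). Its p-value and the standardised CI can disagree near the threshold. The subset has lower power: 73% to 65% by the two-proportion formula at source mean 6.0 and between-subject SD 1.0, which is why it should be supportive only.
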